#### Reporting of SUSARs

All reporting of SUSARs will be done in compliance with the Royal Marsden NHS Foundation Trust current standard operating procedure.

If an SAE is identified as being a SUSAR by the CI, and is fatal or life threatening, it will be reported by the CI to the MHRA, the REC and the Royal Marsden R&D Office within 7 days of being notified of the event.

If an SAE is identified as a SUSAR by the CI, and is not fatal or life threatening, it will be reported by the CI to the MHRA, the REC and the Royal Marsden R&D Office within 15 days of knowledge.

The CI will report any additional relevant information to the MHRA, the REC and the Royal Marsden R&D Office as soon as possible, or within 8 days of the initial report of a fatal/life threatening SUSAR.

#### Serious Adverse Event follow up

The subject must be followed-up until clinical recovery is complete, laboratory tests have returned to normal, or until disease has stabilised. Information on final diagnosis and outcome of SAE which may not be available at the time the SAE is initially reported should be forwarded to the CI.

#### DSURs and Annual Progress Report

The CI is responsible for producing an annual DSUR in liaison with the Pharmacovigilance Officer in the Trust Clinical R&D office, which will be sent to the MHRA. An Annual Progress Report will be submitted to the Research Ethics Committee.

## 5.9.3 Expected adverse events

*Pentoxifylline*: The drug is generally well tolerated, but the following adverse effects have been listed: abnormal laboratory test results; anaphylactic reactions seek; immediate medical advice if you get an anaphylactic reaction; angina; angioedema; bleeding; bronchospasm; diarrhoea; distension of the stomach; faster heart rate; feeling agitated; feeling dizzy; gastrointestinal problems; headaches; hot flushes; irregular heart rate; itching; liver problems; lowered blood pressure; meningitis or meningitislike symptoms; nausea; redness of the skin; sleeping problems; stomach discomfort; thrombocytopenia; urticaria; vomiting

(The frequency of these side effects is unknown. Ref: emc Medicine Guides 28 Jun 11).

*Tocovid SupraBio*: There are no known side effects from Tocovid Suprabio at the dose prescribed in this study.

#### 5.9.4 Recording of adverse events

All adverse events will be documented on the PPALM Adverse Event Log and entered onto the trial database.

# 6 STATISTICAL CONSIDERATIONS

# 6.1 Stratification

Patients will be stratified according to:

- i) the severity of their symptoms (IBDQ-B  $\geq$ 60 vs. IBDQ-B <60)
- ii) average daily fat intake ≥90g fat/day vs. intake <90g fat/day

#### 6.2 **Principal Endpoint**

#### 6.2.1 Primary endpoint

Change at 12 months in the bowel disease subset of the Modified IBDQ Quality of Life questionnaire.

#### 6.2.2 Secondary endpoints

- i) Change at 12 months in rectal IBDQ bleeding score between the two groups in those patients presenting with grade 2, 3 or 4 bleeding.
- ii) Change at 12 months in IBDQ faecal incontinence score between the two groups in those patients presenting with grade 1 or greater incontinence.
- iii) Proportion of items graded as marked or severe (grade 3 or 4).
- iv) Physician assessment of rectal dysfunction using the modified CTCAE Version 4 grading.
- v) Patient self-assessments: QLQ–C30 and CR29 and the Gastrointestinal Symptom Rating Scale.
- vi) Photographic assessments of rectal mucosa.
- vii) Serum fibrosis marker levels.

### 6.3 Sample size

Sample size estimation has been based on changes in the Modified Inflammatory Bowel Disease Questionnaire bowel subset score.

22

#### Primary endpoint

We have previously shown that the IBDQ-B (Inflammatory Bowel Disease Questionnaire is a more sensitive tool than the more commonly used RTOG (Radiation Therapy Oncology Group) and LENT SOM scoring tool (20). It is a questionnaire developed and validated for patients with chronic inflammatory bowel disease, in whom changes in score associated with improved, stable or worsening symptoms have been reported (95). The whole questionnaire is scored out of 224 and gives a bowel health and overall quality of life score. The bowel subset of the IBDQ is scored out of 70, using data from 10 of the 32 questions. Mean (±SD) changes in IBD guestionnaire bowel subset score were 15 ±10 for n=109 with improving symptoms,  $3 \pm 7$  for n=63 with stable symptoms and -3 ±6 for n=8 with worsening symptoms. In the PPALM trial, 10 will be used an estimate of the standard deviation (SD) of the change at 12 months. A difference in guestionnaire score of 7.5 is selected as representing a clinically worthwhile improvement in response to 12 months of Tocovid SupraBio+PTX compared to placebo. We therefore need 99 patients (66 GT3+PTX:33 placebo) for 85% power employing a two-sided 1.67% significance level. We have adopted this level of significance because we wish to keep a 5% overall false positive rate after inclusion of the secondary endpoints relating to changes in bleeding and faecal incontinence.

#### Secondary endpoints

We estimate that 40% of patients will have grade 2, 3 or 4 bleeding, based on our ongoing trial evaluating hyperbaric oxygen in a comparable group of patients, comprising 39 of the 99 patients. The reduction in bleeding in this group of patients will be compared between randomised groups. A reduction in the true proportion of patients showing a fall in their grade of rectal bleeding at 12 months from 70% showing a fall (i.e. 7 in 10) in the Tocovid SupraBio+PTX group to 10% in the placebo group would be detectable (80% power, 1.67% two sided significance level). The pattern of rectal bleeding change in the patients with grade 0-1 bleeding at baseline will be reported but not formally compared between arms. This group is of less interest because mild bleeding does not represent a major impediment to daily living and these individuals are very unlikely to develop serious rectal bleeding over the period of the trial.

We expect that 70% of patients will have grade 1 (35%) or 2 (35%) faecal incontinence, based on the same trial evaluating hyperbaric oxygen, comprising 69 of the 99 patients, and this subgroup can be used to examine the reduction in incontinence. A reduction in the true proportion of patients showing a fall in their grade of faecal incontinence at 12 months from 55% in the Tocovid SupraBio+PTX group to 10% in the placebo group would be detectable (80% power, 1.67% two sided significance level). The pattern of faecal incontinence change in the patients who are grade 0 at baseline will be reported but not formally compared between arms.

The combined false positive rate for the three endpoints described above is 5% (3 x 1.67%).

Our aim is 99 evaluable patients, and 117 patients will therefore be recruited to allow for a 15% drop out rate.

23

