#### 5.4.2 Monitoring of patients during treatment

- i) Adverse events will be recorded and reported as appropriate.
- ii) Any patient can be withdrawn from the study at any time.
- iii) Reasons for withdrawals and any adverse events will be documented and considered in the analysis.
- iv) Patients will be asked to produce a list of current medication (including dosage) before they enter into the study and to keep a medication diary during their Tocovid SupraBio + PTX/placebo therapy. Changes in medication during the 12

15

months of follow up will be collected at the assessment 24 months post randomisation.

- v) Levels of plasma GT3 will be measured at baseline, 3, 6, 9 and 12 months to confirm compliance with drug in those randomised to Tocovid SupraBio/PTX and undetectable levels of GT3 in those allocated placebo. Appropriate Royal Marsden site staff will check compliance in clinic from diary card kept by patients and any leftover trial medication (if applicable).
- 5.5 Follow up assessments during and after treatment (please see table below)
  - Patient self-assessments using IBDQ, the EORTC Quality of Life Questionnaires (QLQ-C30 & QLQ-CR29) and the Gastrointestinal Symptom Rating Scale 3, 6, 9, 12, 18 and 24 months after randomisation.
  - ii) Physician/Clinical Nurse Practitioner grading of late radiation-induced side effects using the modified CTCAE Version 4 form 3, 6, 9, 12 and 24 months after randomisation.
  - iii) Re-assessment with a 7-day food diary at 6 months and 1 year.
  - iv) Flexible sigmoidoscopy with rectal biopsies (optional) and medical photographs of rectal mucosa 12 and 24 months after randomisation.
  - v) Blood levels of IL6, TGF beta and MMP9 3, 6, 9, 12 and 24 months after randomisation as markers of fibrosis.

Procedure	Follow up (months post-randomisation)						
	3	6	9	12	18	24	
Patient self-assessment questionnaires	$\checkmark$	$\checkmark$	$\checkmark$	$\checkmark$	$\checkmark$		
CTCAE Version 4 grading	$\checkmark$	$\checkmark$	$\checkmark$	$\checkmark$		$\checkmark$	
Clinical assessments	$\checkmark$	$\checkmark$	$\checkmark$	$\checkmark$		$\checkmark$	
7 day food diary		$\checkmark$		$\checkmark$			
Rectal photographs				$\checkmark$		$\checkmark$	
Rectal biopsies (optional)						$\checkmark$	
Blood sample	$\checkmark$		$\checkmark$			$\checkmark$	

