#### Secondary Endpoints

The proportions of patients showing a change in rectal IBDQ bleeding score and Faecal incontinence score will be compared using Fisher's exact test.

There will be no formal statistical analysis of the other secondary endpoints but the descriptive nature of these results will be used to strengthen the interpretation of changes in the primary endpoint. Several analyses will be carried out including but not limited to the following:

- i) Changes in modified CTCAE Version 4 grades.
- ii) Standard procedures will be followed for describing quantitative changes in QoL domains using EORTC Quality of Life Questionnaires (QLQ-C30 and CR29).
- iii) Photographs of rectal mucosa will be scored by two experienced endoscopists, who will be blinded with respect to treatment allocation and time of assessment (pre- or post-treatment). The mucosal appearance will be scored using the Wachter classification (51). Disagreement in any scores will be resolved by arbitration after discussion with a third independent endoscopist. Differences in the appearance before and after treatment between the two groups will be assessed.
- iv) Change in levels of 3 serum markers of fibrosis.

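### The two alpha-bearing secondary endpoints are defined three ways, count any change at one visit as response, and are powered on an unsourced 10% placebo rate

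*Protocol*

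**What the plan says.** Only the protocol is at hand; no SAP was shown.

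- **Endpoint lists (5.7.2 and 6.2.2).** The outcomes are 12-month change in the IBDQ bleeding score, "in those patients presenting with grade 2, 3 or 4 bleeding", and in the IBDQ faecal incontinence score, "in those patients presenting with grade 1 or greater incontinence". Patients are therefore selected by grade, while the outcome is a questionnaire score.
- **Sample size (6.3, Secondary endpoints).** The outcome becomes a fall in grade. For bleeding the planning quantity is "A reduction in the true proportion of patients showing a fall in their grade of rectal bleeding at 12 months"; the assumed rates are 70% on active treatment and 10% on placebo. For incontinence it is "A reduction in the true proportion of patients showing a fall in their grade of faecal incontinence at 12 months"; here the assumed rates are 55% and 10%. Both differences are claimed at 80% power and two-sided 1.67%. No minimum fall and no confirming visit is required. The subset shares are credited to the hyperbaric oxygen trial; the 10% is credited to nothing.
- **Analysis (6.4, Secondary Endpoints).** Fisher's exact test is fixed for both endpoints: "The proportions of patients showing a change in rectal IBDQ bleeding score and Faecal incontinence score will be compared using" that test. Neither direction nor size of change is given. Changes in CTCAE grade are listed in the same section among the analyses that get no formal test.
- **Assessments (5.5).** Both scales are collected repeatedly; for the grade the text reads "grading of late radiation-induced side effects using the modified CTCAE Version 4 form 3, 6, 9, 12 and 24 months after randomisation".

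**The concern.** These are formal tests: 6.3 splits the 5% into three parts of 1.67% so that these two can be tested beside the primary endpoint. As written, the quantity powered (fall in grade) is not the quantity tested (change in IBDQ score). Read literally, the tested quantity counts a worsening as well as an improvement.

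There is also a problem of efficiency. The subsets are chosen because a baseline grade was high. If any later fall counts, some patients fall with no real change, because the baseline reading was high by chance or the later one low. On the grade scale this is most direct for patients at the lowest eligible grade, who leave the entry range with a one-step fall. On the plan's 35%/35% split that is half of the incontinence subset. On the IBDQ scale selection and outcome differ, so that threshold argument does not carry over directly, but any one-step difference at one visit still counts.

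Noise responders appear in both arms and shrink the contrast. If the placebo rate is well above 10%, a negative result on either test would say little about the drug.

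**Working it through.** **Inputs from the protocol.** 99 evaluable patients, 2:1 allocation, two-sided 1.67%. Incontinence: 69 patients (46:23), 55% vs 10%, grade shares 35% (grade 1) and 35% (grade 2), leaving 30% at grade 0. Bleeding: 39 patients (26:13), 70% vs 10%, 40% at grade 2 or above, split within that not given.

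**1. The plan's own figure.** The protocol claims 80% power for both comparisons.

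| Method | Incontinence 46:23 | Bleeding 26:13 |
|---|---|---|
| Normal approximation | 94.1% | 94.3% |
| Fisher, exact enumeration | 92.7% | 90.4% |

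The 80% is not reproduced. It is conservative at the planned rates, so the plan has some slack.

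**2. How often would patients fall a grade with no true change?** Assumption, not in the documents: baseline and 12-month severity are bivariate normal with correlation r and are cut at the baseline grade shares. With c_g the lower cut of grade g and m the lowest eligible grade,

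P(fall) = Σ over g ≥ m of [Φ₂(c_{g+1}, c_g; r) − Φ₂(c_g, c_g; r)] ÷ P(grade ≥ m).

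For incontinence the cuts are Φ⁻¹(0.30) and Φ⁻¹(0.65). For bleeding I assume 30% each at grades 0 and 1 and vary the split above.

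| r | Incontinence 30/35/35 | Bleeding, all at grade 2 | Bleeding, 30% grade 2 and 10% grade 3 |
|---|---|---|---|
| 0.95 | 13.0% | 12.2% | 17.7% |
| 0.90 | 18.2% | 17.4% | 25.0% |
| 0.80 | 25.0% | 24.8% | 34.7% |
| 0.70 | 29.6% | 30.6% | 41.4% |

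An even 20%/20% split of grades 2 and 3 gives 20.7% to 43.5%. A 10% rate needs r of about 0.97 for incontinence and 0.967 to 0.989 for bleeding, depending on the split.

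**3. Power at higher placebo rates (Fisher, 1.67%).** Two versions bracket the loss. Version A holds the active rate at 55% or 70%. Version B lets noise act in both arms and keeps the plan's implied effect among patients who would not otherwise fall: e = (0.55 − 0.10)/0.90 = 0.50 and e = (0.70 − 0.10)/0.90 = 0.667, so the active rate is c + (1 − c)e at placebo rate c. At c = 0.30 that is 0.30 + 0.70 × 0.50 = 0.65 for incontinence and 0.30 + 0.70 × 0.667 = 0.767 for bleeding.

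| Placebo rate | Incontinence A | Incontinence B | Bleeding A | Bleeding B |
|---|---|---|---|---|
| 10% | 93% | 93% | 90% | 90% |
| 15% | 80% | 86% | 80% | 83% |
| 18% | 70% | 81% | 73% | 79% |
| 20% | 63% | 77% | 68% | 76% |
| 30% | 28% | 58% | 42% | 62% |

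Power drops to 80% at a placebo rate of about 15% in version A for both endpoints. In version B it does so at about 18% (incontinence) and 17% (bleeding).

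**4. Does a baseline-adjusted comparison help?** Simulation with an assumed effect (latent drop of 1.2 SD in 60% of active incontinence patients or 80% of active bleeding patients), comparing Fisher on any fall with ANCOVA of the 12-month grade on baseline grade, at reliability 0.7/0.8/0.9:

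- Incontinence: Fisher 51/64/83%, ANCOVA 66/75/87%.
- Bleeding: Fisher 50/61/82%, ANCOVA 75/83/94%.

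Type I error stayed at about 1.5-1.7%. The size of the gain depends on the assumed effect.

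**The case against.** The strongest reply is that the noise percentages are not evidence. The protocol gives no test-retest reliability, no placebo response rate and no split of bleeding into grades 2, 3 and 4. Some of its text argues for stability: symptoms must have persisted through three months of treatment after optimal assessment, incontinence grades 1 and 2 are anchored to pad use, and section 1.2 calls most such syndromes progressive and irreversible. That stands as a limit on the figures. It does not support 10% either: it concerns true course rather than grading noise, section 1.2 also allows that some symptoms improve with time, and entry is open to grade 1 with difficult intermittent symptoms.

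A second reply is that a responder proportion with Fisher's test is conventional in subsets of 39 and 69, and that response thresholds can be left to a SAP. This partly stands: the test is valid, and baseline adjustment is a gain in efficiency. But the protocol itself fixes Fisher's test on an undirected change and contradicts itself on the outcome scale, which a SAP cannot settle without departing from one section or another.

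A reader might infer three stronger things. That the false positive rate is inflated: it is not, since noise affects both randomised arms alike. That power falls to 28% and 42% at 30% placebo: those figures freeze the active arm, although noise would raise it too, giving 58% and 62%. That the claimed power is simply unavailable: at 13% placebo, incontinence power is still 86% even with the active arm frozen.

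**Conclusion.** The point holds in limited form. The conflict between 5.7.2/6.2.2, 6.3 and 6.4 over what is measured is plain on the text and rests on no assumption. So does the absence of any source for the 10% placebo rate.

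The size of the noise problem is illustrative. With correlation 0.70 to 0.95 and no true change, 13-30% of the incontinence subset and about 12-41% of the bleeding subset would fall by at least one grade; the bleeding range also depends on the assumed split. These figures apply to the grade scale only. The consequence is dilution and lost power. The claimed 80% survives to a placebo rate of about 15% (active rate held) or 17-18% (noise in both arms), and is about 77% and 76% at 20% and 58% and 62% at 30% in the latter case. The protocol should be changed, but nothing here undermines the validity of the tests or the primary endpoint.

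**What to change.** 1. Reconcile 5.7.2, 6.2.2, 6.3 and 6.4 to one outcome scale per endpoint, either the IBDQ score or the grade, and state that the change of interest is improvement.
2. In 6.4, compare the 12-month value on that scale between arms within the baseline-selected subset, adjusted for the baseline value on the same scale (ANCOVA or proportional odds), at two-sided 1.67%. Report the proportion improved descriptively.
3. In 6.3, replace power at a 10% placebo rate alone with power over a range such as 10-30%, stating how the active rate is assumed to move.

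If the grade is kept, the mean of the pre-entry and pre-treatment CTCAE grades, both already in the schedule of events, could serve as the baseline covariate. This does not work for the IBDQ score, which is scheduled only once before treatment.

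The cost is wording: no new visits, data or patients. A mean difference or odds ratio is less simple to read than a responder proportion, and the stated secondary power will look less favourable.

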# 5.3 Allocation of treatment

Treatment allocation will be in a 2:1 ratio of Tocovid SupraBio+PTX treatment: matched placebo and will be based on computer generated random permuted blocks. Patients will be asked to start their allocated treatment the day after randomisation. Pharmacy will be informed of the randomisation and hold records in the pharmacy file.

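### Section 6.3 quotes 80% power for the bleeding and incontinence comparisons, but its own inputs give about 90% and 93%: a conservative misstatement that leaves the sample size untouched

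*Protocol*

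**What the plan says.** The subsection on secondary endpoints in Protocol section 6.3 expects about 40% of patients to have grade 2 to 4 rectal bleeding, "comprising 39 of the 99 patients", and about 70% to have grade 1 or 2 faecal incontinence, "comprising 69 of the 99 patients".

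For bleeding, the contrast in the proportion whose grade falls by 12 months runs "from 70% showing a fall (i.e. 7 in 10) in the Tocovid SupraBio+PTX group to 10% in the placebo group". For incontinence, the plan says that a contrast "from 55% in the Tocovid SupraBio+PTX group to 10% in the placebo group would be detectable (80% power, 1.67% two sided significance level"). The bleeding sentence closes with the same claim: the contrast "would be detectable (80% power, 1.67% two sided significance level").

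Two further inputs are given elsewhere. Section 5.3 says "Treatment allocation will be in a 2:1 ratio of Tocovid SupraBio+PTX treatment: matched placebo". Section 6.4 names Fisher's exact test for the bleeding and incontinence comparisons.

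**The concern.** A power statement should follow from its sample size, proportions, level and test. Here all of these are given or directly implied, yet both comparisons are quoted at 80% although they differ in subgroup size and in effect. A quick check puts both well above 80%.

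What is at stake is limited to how readers understand the trial's sensitivity. These are the two secondary endpoints that are formally tested, each at 1.67%. If the proportions are right, someone using section 6.3 to interpret a null result would think the smallest effect detectable at 80% power is larger than it is. If the 80% is right, one of the other stated inputs must be wrong, and the text does not say which.

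**Working it through.** **Inputs**

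| Input | Bleeding | Incontinence | Source |
|---|---|---|---|
| Evaluable patients | 39 | 69 | Section 6.3 (0.40 × 99 = 39.6; 0.70 × 99 = 69.3) |
| Active vs placebo, fall in grade | 0.70 vs 0.10 | 0.55 vs 0.10 | Section 6.3 |
| Two-sided level | 0.0167 | 0.0167 | Section 6.3 |
| Test | Fisher's exact | Fisher's exact | Section 6.4 |
| Split | 26:13 | 46:23 | Assumed from the 2:1 ratio in section 5.3 |
| Stated power | 80% | 80% | Section 6.3 |

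The 39 and 69 are shares of the 99 evaluable patients, so the 15% drop-out allowance is not deducted again.

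**Formula.** Let a and b be the numbers with a fall in grade in the active arm (size n1) and the placebo arm (size n2). Then

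power = Σ over b of P(b | n2, p2) × P(Fisher p ≤ 0.0167 | b),

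where the second factor sums the Binomial(n1, p1) probabilities of all a for which the test rejects, given b.

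**Bleeding, 26:13, 0.70 vs 0.10**

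| b | P(b) | Smallest a favouring active that rejects | P(reject given b) | Product |
|---|---|---|---|---|
| 0 | 0.2542 | 10 | 0.9998 | 0.2541 |
| 1 | 0.3672 | 13 | 0.9906 | 0.3637 |
| 2 | 0.2448 | 16 | 0.8747 | 0.2141 |
| 3 | 0.0997 | 18 | 0.6274 | 0.0626 |
| 4 | 0.0277 | 20 | 0.2965 | 0.0082 |
| 5 | 0.0055 | 21 | 0.1626 | 0.0009 |

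The sum is 0.904, with negligible terms beyond b = 5.

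**Incontinence, 46:23, 0.55 vs 0.10**

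| b | P(b) | Smallest a favouring active that rejects | P(reject given b) | Product |
|---|---|---|---|---|
| 0 | 0.0886 | 11 | 1.0000 | 0.0886 |
| 1 | 0.2265 | 14 | 0.9998 | 0.2264 |
| 2 | 0.2768 | 18 | 0.9895 | 0.2739 |
| 3 | 0.2153 | 20 | 0.9569 | 0.2060 |
| 4 | 0.1196 | 23 | 0.7970 | 0.0953 |
| 5 | 0.0505 | 25 | 0.5954 | 0.0301 |
| 6 | 0.0168 | 27 | 0.3629 | 0.0061 |
| 7 | 0.0045 | 30 | 0.1059 | 0.0005 |

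The sum is 0.927, again with negligible further terms.

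The gaps from the stated figure are 90.4 − 80 = 10.4 points and 92.7 − 80 = 12.7 points.

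**Could another method give 80%?** Same inputs and split:

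| Method | Bleeding | Incontinence |
|---|---|---|
| Fisher, doubled one tail | 89.7% | 91.2% |
| Chi-square with Yates correction | 85.4% | 89.7% |
| Continuity-corrected formula | 86.6% | 88.9% |
| Chi-square, uncorrected | 94.1% | 94.3% |
| Normal, pooled variance | 94.3% | 94.1% |
| Arcsine | 93.9% | 94.8% |
| Normal, unpooled variance | 99.4% | 98.9% |

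The lowest values are 85.4% and 88.9%, so none reproduces 80%. Put the other way, 80% Fisher power at the stated proportions needs a 2:1 total of 33 for bleeding (82.8%) and 51 for incontinence (80.6%), against 39 and 69.

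**Chance imbalance.** Drawing the 39 or 69 at random from 66:33 (hypergeometric) and averaging gives 89.4% and 92.2%.

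**Detectable active proportion against 10% placebo, Fisher, 80% power**

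- Bleeding: 0.63 gives 79.3%, 0.634 gives 80.0% and 0.64 gives 81.1%. This is about 64%, against 70% stated (70 − 64 = 6 points).
- Incontinence: 0.48 gives 80.1%. This is about 48%, against 55% stated (55 − 48 = 7 points).

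**Which input might differ?** Changing only the placebo proportion to 0.15 gives 80.1% for bleeding and 80.2% for incontinence.

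**The case against.** The strongest reply is that the discrepancy changes no decision. The stated differences are detectable with at least 80% power, section 6.3 bases the sample size on the bowel subset score, and the level, the test and the conduct of the trial are unaffected. All of this stands, and it sets the severity.

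A second reply is that the subgroup splits are not fixed, because section 6.1 stratifies by IBDQ-B score and fat intake and not by bleeding or incontinence. That is true. For bleeding, power falls to about 79% if only 9 of the 39 are on placebo, and rises to about 93% with 18. But a planning figure should reflect the expected split, and averaging over splits still gives 89% and 92%. Any restated figure should name the split as an assumption.

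Third, section 6.3 powers a fall in grade, whereas section 6.4 compares proportions with a change in IBDQ bleeding and incontinence scores. The recalculation covers the quantity described in 6.3. It does not settle which definition applies.

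Three stronger readings are tempting, and the documents do not support them:

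- **That these power figures justify giving each endpoint a third of the 5%.** Section 6.3 gives another reason: control of the overall false positive rate across three comparisons.
- **That the two comparisons are underpowered because placebo response may exceed 10%.** No source is given for the 10%, and power does drop at higher rates: with the active rate unchanged, 20% placebo gives about 68% and 63%. But the protocol offers no higher rate, so such values are illustrations and not evidence of an error.
- **That the 10% is a misprint for 15%.** The match at 15% for both endpoints is suggestive only. It is a reason to ask.

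**Conclusion.** The point holds as a low-severity arithmetic error. At the protocol's own proportions, subgroup sizes, level and named test, power is about 90% for bleeding and 93% for incontinence, not 80%. Power is understated by 10 to 13 points, and the effects detectable at 80% power are overstated by 6 to 7 points.

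The conclusion rests on one assumption, a 2:1 split within each subgroup, and it survives averaging over random splits and every common alternative method tried. The direction is conservative as long as the 10% placebo rate is what was planned.

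**What to change.** First confirm from the planning records which placebo proportion and method were used. If 10% stands, amend the two sentences in section 6.3 in one of two ways:

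- Keep 70% vs 10% and 55% vs 10%, and state the power as about 90% and 93% by Fisher's exact test, assuming a 2:1 split within each subgroup.
- Keep 80% power, and give the detectable contrasts as about 64% vs 10% for bleeding and 48% vs 10% for incontinence, on the same assumption.

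If the records show 15%, correct the placebo proportion instead and leave the 80%. Power at other placebo rates may be added as illustration but is not needed.

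The cost is two sentences. The sample size, significance levels and planned test do not change.

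### The fixed 1.67% split over three endpoints is valid, but Holm's step-down procedure keeps the same 5% familywise error, is never less powerful and needs no extra patients

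*Protocol*

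**What the plan says.** Protocol section 6.3 (Sample size, Primary endpoint) sizes the trial as follows: "We therefore need 99 patients (66 GT3+PTX:33 placebo) for 85% power employing a two-sided 1.67% significance level". The inputs are an SD of 10 ("10 will be used an estimate of the standard deviation (SD) of the change at 12 months") and a difference of 7.5 points. The reason given for the reduced level is that "we wish to keep a 5% overall false positive rate after inclusion of the secondary endpoints relating to changes in bleeding and faecal incontinence".

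The Secondary endpoints part of section 6.3 applies the same 1.67% to bleeding and to faecal incontinence, each in a subgroup defined at baseline, and adds up: "The combined false positive rate for the three endpoints described above is 5% (3 x 1.67"%).

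Section 6.4 names the tests: Mann-Whitney or unpaired t-test for the primary, and Fisher's exact test for the two secondaries. It gives no ordering, no step-down and no passing on of unused alpha.

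**The concern.** The stated aim is a 5% error rate over three tests. As section 6.3 reads, each test stays at 1.67% whatever the other two show, so the primary endpoint keeps one third of the 5% even when both secondaries are clearly positive.

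Holm's procedure reaches the same aim on the same three p-values and can only add rejections. Suppose the primary p-value is 0.03, one secondary has p≤1.67% and the other p≤2.5%. The fixed split declares the primary endpoint negative. Holm rejects it, within the 5% that the protocol sets itself. In a trial planned with 33 evaluable patients in the smaller arm, power available without recruiting anyone is worth having.

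**Working it through.** **Inputs from Protocol section 6.3.** Difference 7.5, SD 10, 66:33, two-sided 1.67%. Bleeding subgroup 39 of 99 (26:13 at 2:1), 70% vs 10%. Incontinence subgroup 69 of 99 (46:23 at 2:1), 55% vs 10%. Each secondary is stated to have 80% power. The correlation between endpoints is not given, so 0 to 0.5 is assumed.

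**1. The plan's own figures.**
- SE = 10 × √(1/66 + 1/33) = 2.132, so the expected z is 7.5/2.132 = 3.52.
- Power at 1.67%: 85.8% by noncentral t with 97 df, 87.0% by the normal approximation. The stated 85% is reproduced; 64:32 would give 84.6%.
- Dropout: 99/0.85 = 116.5, rounded up to 117.
- Error: 3 × 0.05/3 = 5% as an upper bound; 1 − (1 − 0.05/3)³ = 4.9% if the tests were independent.

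**2. Why Holm dominates.** Order the p-values p(1) ≤ p(2) ≤ p(3). Reject the first if p(1) ≤ 5%/3, then the second if p(2) ≤ 5%/2, then the third if p(3) ≤ 5%, and stop at the first failure. Any p-value at or below 1.67% passes its step, because every threshold is at least 1.67% and every smaller p-value also passes. So everything the fixed split rejects, Holm rejects. Familywise control at 5% does not depend on the correlation.

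**3. Size of the gain for the primary endpoint.** Simulation of three normal test statistics, 400,000 per scenario. The primary mean is 3.52. A secondary with a real effect has mean 2.394 + 0.842 = 3.24, which is its stated 80% power at 1.67%. Ranges cover correlations 0 to 0.5.

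| True effects | Fixed split | Holm |
|---|---|---|
| All three as planned | 87% | 91-93% |
| Primary and one secondary | 87% | about 89% |
| Primary only | 87% | 87% |
| All shrunk in proportion (primary 5.5 points, means × 5.5/7.5) | 57% | about 64% |

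In the first row each secondary rises from 80% to 87-88%.

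**4. The same check with the tests named in section 6.4.** t-test at 66:33, Fisher's exact test at 26:13 and 46:23, planned effects, 40,000 trials per scenario, correlation 0 / 0.5:
- Primary: 85.5% to 93.0% / 85.7% to 92.7%.
- Bleeding: 90.5% to 96.5% / 90.3% to 96.1%.
- Incontinence: 92.9% to 97.3% / 92.7% to 96.9%.

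The secondaries start above 80% here because the stated rates and subgroup sizes give Fisher's test about 90% and 93% power at an exact 2:1 split.

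**5. Error control.** With all three null hypotheses true and independent continuous p-values, the familywise error is 4.9% under both procedures. With the primary null true and both secondaries certain to be rejected, Holm's false positive rate for the primary is 5.0%.

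**The case against.** Nothing in section 6.3 is miscalculated. The reason for 1.67% is stated, the split adds up to 5%, and the trial is sized for it. A reader might infer that the false positive rate is wrong or that the primary endpoint is underpowered. The documents support neither, because both figures reproduce. This stands: the point concerns efficiency, not an error.

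Every mention of 1.67% is in the sample size section, and sizing at one third of alpha is compatible with Holm, whose first step is also 1.67%. A statistical analysis plan that is not shown could add the step-down. That is possible, but section 6.3 says that this level has been adopted and sums three fixed shares, so the natural reading is a fixed level for each test.

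The gain is conditional. A reader might infer that Holm hands the full 5% back to the primary endpoint. It does so only when both secondaries have already been rejected, and the planned secondary effects are large ("from 70% showing a fall (i.e. 7 in 10) in the Tocovid SupraBio+PTX group to 10% in the placebo group" for bleeding). If neither secondary responds, the primary gains practically nothing. A reader might also quote a rise from 57% to 70% at a true difference of 5.5 points, but that figure leaves both secondaries at full planned effect while the primary weakens. Under proportional shrinkage the rise is to about 64%.

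Finally, Holm lets the decision on the primary endpoint depend on two subgroup endpoints. Testing the primary first at 5% would give it 93.6% power regardless, but the secondaries could then be tested only after a positive primary. That is a legitimate alternative with a different trade-off. Unlike Holm, it is not at least as powerful as the current rule for every endpoint.

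**Conclusion.** The point holds as a worthwhile improvement to a valid, correctly sized plan. The fixed split is dominated: Holm has the same 5% familywise control under any dependence and is never less powerful for any endpoint.

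At the planned effects, the chance of missing a real primary effect falls from about 13-14% to 7-9%. The benefit shrinks to two or three percentage points with one real secondary effect and to practically nothing with none. It is therefore not a general promise of more power for every endpoint.

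The sizes rest on the protocol's effects and SD, an exact 2:1 split within the subgroups, and the assumed correlations of 0 to 0.5. That Holm dominates the fixed split rests on none of these.

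**What to change.** In Protocol section 6.3, replace the 3 × 1.67% statement with: *The three p-values will be tested by Holm's step-down procedure at a familywise two-sided 5%.* Repeat the rule in section 6.4, where the tests are named. Keep 99 evaluable and 117 recruited patients, and describe 85% as the minimum power for the primary endpoint at the design effect.

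The cost is one sentence in two places, made before unblinding. The one drawback is in the confidence intervals: a 98.33% interval may include no effect when Holm rejects. Such intervals can still be reported, labelled as not matching the test decision.
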